APPENDIX 3. PHARMACOKINETIC AND ANTIDRUG ANTIBODY BLOOD SAMPLING

Study Day	Day 1			Day 2	Day 3	Day 4	Day 5	Day 8	Day 15	Day 22	Day 29	Day 43	Day 57	Day 71	Day 85	Day 113/ EOS
	0 (predose)	EOI	6	24	48	72	96	168	336	504	672	1008	1344	1680	2016	2688
Hours post the start of infusion	0 (predose)	EOI	6	24	48	72	96	168	336	504	672	1008	1344	1680	2016	2688
Window Period (hours)	-60 min to predose	Within 30 min after EOI	±2	±6	±6	±6	±6	±6	±24	±24	±24	±48	±48	±48	±48	±48
PK blood sampling	X	X	X	X	X	X	X	X	X	X	X	X	X	X	X	X
ADA sampling	X								X		X		X		X	X

Abbreviations: ADA, antidrug antibody; EOI, end of infusion; EOS, End-of-Study; min, minutes; PK, pharmacokinetics.

Note: Sample collection must be from the opposite arm that is used for study drug infusion. Refer to laboratory manual for detailed collection instructions.

APPENDIX 4. CLINICAL LABORATORY ASSESSMENTS

Clinical chemistry	Hematology	Coagulation	Urinalysis ^a
Alkaline phosphatase Alanine aminotransferase Aspartate aminotransferase Albumin Total bilirubin Direct bilirubin Blood urea nitrogen or urea Potassium Sodium Total calcium Creatinine Glucose Lactate dehydrogenase Total protein Magnesium Lipase Amylase	Red blood cell count Hematocrit Hemoglobin Platelet count White blood cell count with differential (both absolute count and percentage) 
 • Lymphocyte count • Neutrophils • Monocytes • Eosinophils • Basophils 	Prothrombin time Partial thromboplastin time or activated partial thromboplastin time International normalized ratio	Specific gravity pH Glucose Protein Blood Ketones Bilirubin Urobilinogen Nitrite Leukocyte esterase
Other Screening Tests			

 • Follicle-stimulating hormone and estradiol (as needed for female subjects who are < 55 years of age with no spontaneous menses for ≥ 12 months to identify the status of no childbearing potential) • Urine (drugs screen [to include at minimum: amphetamines, barbiturates, benzodiazepines, cocaine, opiates, methamphetamines, methadone, methyl enedioxy methamphetamine, phencyclidine, and tetrahydrocannabinol]) • Breath test (alcohol screen) • Highly sensitive (serum/urine) human chorionic gonadotropin pregnancy test (as needed in female subjects of childbearing potential) • Serology: 
 - HIV antibody - hepatitis B surface antigen, hepatitis B core antibody, hepatitis C virus antibody - IgG antibodies against SARS-CoV-2 • Virology: nasopharyngeal or oropharyngeal swab for COVID-19 rRT-PCR test 
The results of each test must be entered into the CRF.
			

Abbreviations: COVID-19, Coronavirus Disease 2019; CRF, case report form; HIV, human immunodeficiency virus; Ig, immunoglobulin; pH, negative of the logarithm to base 10 of the activity of the (solvated) hydronium ion; rRT-PCR, real-time reverse transcription polymerase chain reaction; SARS-CoV-2, severe acute respiratory syndrome coronavirus 2.

^a The urine microscopy will be performed if the urinalysis parameter, such as leukocyte esterase, is out of normal range.

APPENDIX 5. CONTRACEPTION GUIDELINES AND DEFINITIONS OF “WOMEN OF CHILDBEARING POTENTIAL”, “NO CHILDBEARING POTENTIAL”

Contraception Guidelines

The Clinical Trials Facilitation Group’s recommendations related to contraception and pregnancy testing in clinical trials include the use of highly effective forms of birth control (Clinical Trials Facilitation Group 2014). These methods include the following:

- Combined (estrogen- and progestogen-containing) hormonal contraception associated with the inhibition of ovulation
 - Oral, intravaginal, or transdermal
- Progestogen-only hormonal contraception associated with the inhibition of ovulation:
 - Oral, injectable, or implantable
Note: Oral birth control pills are not considered a highly effective form of birth control, and if they are selected, they must be used with a second, barrier method of contraception such as condoms with or without spermicide.
- Intrauterine device
- Intrauterine hormone-releasing system
- Bilateral tubal occlusion
- Vasectomized male partner
Note: This is only considered a highly effective form of birth control when the vasectomized partner is the sole partner of the study participant and there has been a medical assessment confirming surgical success.
 - A sterile male is one for azoospermia has been demonstrated in a semen sample examination as definitive evidence of infertility.
- Sexual abstinence (defined as refraining from heterosexual intercourse during the entire period of exposure associated with the study treatment).
NOTE: Total sexual abstinence should only be used as a contraceptive method if it is in line with the subject’s usual and preferred lifestyle. Periodic abstinence (eg, calendar, ovulation, symptothermal, or postovulation methods), declaration of abstinence for the duration of exposure to study drug(s), and withdrawal are not acceptable methods of contraception.

Of note, barrier contraception (including male and female condoms with or without spermicide) is not considered a highly effective method of contraception and if used, this method must be combined with another acceptable method listed above.

Definitions of “Women of Childbearing Potential,” “Women of No Childbearing Potential”

As defined in this protocol, “women of childbearing potential” are female subjects who are physiologically capable of becoming pregnant.

[figure not shown]
Conversely, “women of no childbearing potential” are defined as female subjects meeting any of the following criteria:

- Surgically sterile (ie, through bilateral salpingectomy, bilateral oophorectomy, or hysterectomy)
- Postmenopausal, defined as:
 - ≥ 55 years of age with no spontaneous menses for ≥ 12 months OR
 - < 55 years of age with no spontaneous menses for ≥ 12 months AND with a postmenopausal follicle-stimulating hormone (FSH) concentration > 30 IU/mL and all alternative medical causes for the lack of spontaneous menses for ≥ 12 months have been ruled out, such as polycystic ovarian syndrome, hyperprolactinemia, etc.

If an FSH measurement is required to confirm postmenopausal state, concomitant use of hormonal contraception or hormonal replacement therapy should be excluded.

Adapted from [Clinical Trials Facilitation Group 2014](#).

Signature Page for VV-CLIN-032575 v1.0

Approval	 Clinical Development 04-Aug-2020 14:37:18 GMT+0000
----------	--

Signature Page for VV-CLIN-032575 v1.0

1. INTRODUCTION

The purpose of this statistical analysis plan (SAP) is to describe the procedures and the statistical methods that will be used to analyze and report results for BGB-DXP593-101, A First-in-Human, Randomized, Double-Blind, Placebo-Controlled, Single Dose Escalation Study to Evaluate the Safety, Tolerability, Pharmacokinetics, and Immunogenicity of SARS-CoV-2 Neutralizing Antibody BGB-DXP593 in Healthy Subjects. The focus of this SAP is for the planned final analysis specified in the study protocol.

Reference materials for this statistical plan include the BGB-DXP593-101 Original Protocol dated on 04 August 2020.

2. STUDY OVERVIEW

This is a first-in-human, randomized, double-blind, placebo-controlled, single dose escalation study to investigate the safety, tolerability, pharmacokinetic (PK), and immunogenicity of BGB-DXP593 in healthy subjects.

Two dose levels are planned for eligible subjects to receive a single intravenous dose of study drug (ie, BGB-DXP593 or placebo) at 10 mg/kg or 30 mg/kg, respectively. Another higher dose level will be allowed for dose escalation.

Enrollment will begin at the 10 mg/kg dose level. Escalation to the next dose level will occur 7 days after the last subject at the current dose level has received the study drug, and the safety, laboratory data have been reviewed.

At each dose level, eligible subjects will be randomized at a 3:1 ratio (6 active: 2 control) to the active arm for receiving BGB-DXP593 or to the control arm for receiving the same volume of placebo (ie, normal saline), respectively.

The sentinel dosing will be adopted for each dose level. In the other words, 2 eligible subjects will be randomized at a 1:1 ratio (1 active: 1 control) to receive BGB-DXP593 or placebo on Day 1; and the remaining subjects will be randomized at a 5:1 ratio (5 active: 1 control) to receive BGB-DXP593 or placebo at least 48 hours later, provided satisfactory safety and tolerability is demonstrated for the first 2 subjects randomized and dosed at the dose level.

Subjects are expected to be available for follow-up visits until Day 113 of the study. Subjects will be replaced if they cannot complete the infusion. Subjects may be replaced if they discontinue from the study before Day 29.

Subjects will be monitored for safety, tolerability, PK and immunogenicity of BGB-DXP593 throughout the study.

3. STUDY OBJECTIVES

3.1. Primary Objective

• To investigate the safety and tolerability of BGB-DXP593 administered intravenously as a single dose in healthy subjects

3.2. Secondary Objectives

- To characterize the pharmacokinetic (PK) profile of BGB-DXP593 administered intravenously as a single dose at each dose level in healthy subjects
- To evaluate the potential immunogenicity of BGB-DXP593 administered intravenously as a single dose at each dose level in healthy subjects

4. STUDY ENDPOINTS

4.1. Primary Endpoint

 Incidence and severity of treatment-emergent adverse events (TEAEs) and treatment-emergent serious adverse events (SAEs)

4.2. Secondary Endpoints

- Changes in vital signs and 12-lead electrocardiogram (ECG) parameters from baseline
- Incidence and magnitude of clinical laboratory abnormalities
- Characterize PK concentration-time profile and PK parameters for BGB-DXP593: C_{max}, AUC_t, AUC_{inf}, AUC₀₋₂₉, t_{max}, t_{1/2}, CL, and V_z as appropriate
- Clinical immunogenicity of BGB-DXP593 evaluated through the detection of ADA over time

5. SAMPLE SIZE CONSIDERATIONS

A sample size of 8 subjects at each dose level (6 active and 2 control) totaling up to 30 subjects (including possible replacement) is not based on any statistical considerations. The sample size is based on the clinical consideration to provide safety and tolerability information and pharmacological considerations with the need to minimize exposure to healthy subjects at each dose level. No formal inferential statistics will be applied to the safety or PK data.

6. STATISTICAL METHODS

6.1. Analysis Sets

The Safety Analysis Set will include all the subjects who received the study drug, and subjects will be grouped by actual treatment received. The Safety Analysis Set is used for all safety analyses.

The PK Analysis Set will include all the subjects who received the study drug and had any measurable concentration of study drug. The PK Analysis Set will be used for PK analyses.

BeiGene 12 May 2021

The ADA Analysis Set include all the subjects who received the study drug and in whom both baseline ADA and at least 1 postbaseline ADA results are available. The ADA Analysis Set is used for immunogenicity analyses.

6.2. Data Analysis General Considerations

6.2.1. Definitions and Computations

Study Day: study day will be calculated in reference to the date of the dose of study drug. For assessments conducted on or after the date of the dose of study drug, study day will be calculated as (assessment date – the date of the dose of study drug + 1). For assessments conducted before the date of the dose of study drug, study day will be calculated as (assessment date – the date of the dose of study drug). There is no study day 0.

In the situation where the event date is partial or missing, the date will appear partial or missing in the listings. Study day and any corresponding durations will be presented based on the imputations specified in Appendix A.

Baseline: baseline is defined as the last non-missing value collected before the dose of study drug.

All calculations and analyses will be conducted using SAS® Version 9.4 or higher.

All subjects who received placebo from different cohorts will be pooled together into the placebo arm.

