4.2. Exclusion Criteria

Subjects who meet any of the following criteria will be excluded from this study:

Medical Histories or Conditions

1. History or presence of cardiovascular, respiratory, hepatic, renal, gastrointestinal, endocrinological, hematological, or neurological disorders capable of significantly altering the absorption, metabolism, or elimination of drugs, constituting a risk to the subject when taking the study drug; or interfering with the interpretation of data
2. Systolic blood pressure $>$ 150 mmHg at screening
3. Any malignancy within the past 5 years except for basal cell or squamous epithelial carcinomas of the skin that have been resected with no evidence of metastatic disease for 3 years

4. Any history of a severe allergic reaction prior to enrollment that has a reasonable risk of recurrence during the study
5. Have a medical history of SARS infection
6. Any acute fever disease or infections
7. Any chronic or clinically significant medical condition that, in the opinion of the investigator, would jeopardize the safety or rights of the subject, including but not limited to: diabetes mellitus type I, chronic hepatitis; or clinically significant forms of: drug or alcohol abuse, asthma (except for childhood asthma), autoimmune disease, psychiatric disorders, or heart disease
8. Platelet disorder or other bleeding disorder may cause injection contraindication
9. Alanine aminotransferase and/or aspartate aminotransferase $> 1.5 \times$ upper limit of normal (ULN)
10. Bilirubin $> 1.5 \times$ ULN (isolated bilirubin $> 1.5 \times$ ULN is acceptable if bilirubin is fractionated and direct bilirubin $< 35\%$)
11. Current or chronic history of liver disease or known hepatic or biliary abnormalities (with the exception of Gilbert's syndrome or asymptomatic gallstones)
12. Average Fridericia's formula (QTcF) > 450 msec (based on triplicate ECGs)
 - NOTE A: The QTc is the QT interval corrected for heart rate according to QTcF, and/or another method. It is either machine-read or manually over-read.
 - NOTE B: The specific formula used to determine eligibility or discontinuation for an individual participant should be determined prior to initiation of the study. In other words, several different formulas cannot be used to calculate the QTc for an individual participant and then the lowest QTc value used to include or discontinue the participant.

Prior/Concomitant Therapy

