8.2.4. Electrocardiograms

For safety monitoring purposes, the investigator must review, sign, and date all ECG tracings. Paper or electronic copies of ECG tracings (per local practice) will be kept as part of the subject's permanent study file at the site.

The subject should rest in a semirecumbent or supine position for ≥ 10 minutes in the absence of environmental distractions that may induce changes in heart rate (eg, television, radio, conversation) before each ECG collection.

At each timepoint (see [Appendix 1](#)), 3 consecutive 12-lead ECGs will be performed approximately 2 minutes apart to calculate heart rate and measure QT and QTcF intervals.

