- ^b The EOS Visit will be conducted within 7 days after a premature study discontinuation. The Day 113 Visit is the EOS Visit for subjects who complete all the previously planned study visits.
- ^c The Safety Follow-up Visit is only for subjects who discontinue the study within 30 days after the dose of study drug. The Safety Follow-up Visit will be conducted on 30 days after the dose of study drug (± 3 days). If the premature discontinuation from study occurs within 7 days prior to the timepoint of 30 days after the dose of study drug, the Safety Follow-up Visit could be combined with the EOS Visit as appropriate.
- ^d The informed consent must be obtained before performing any study-specific procedures. Consent must be obtained using the current version of the form approved by the Independent Ethics Committee/Institutional Review Board.
- ^e Follicle-stimulating hormone and estradiol assessments will be performed on female subjects who are < 55 years of age with no spontaneous menses for ≥ 12 months to identify the status of no childbearing potential. Female subjects of no childbearing potential, and female subjects of childbearing potential who are willing to use a highly effective method of birth control are eligible to participate.
- ^f Subjects will be randomized into either the active arm or control arm via IRT. Randomization will occur after the admission on Day -1 and before the dose of study drug on Day 1.
- ^g The dose will be based on the subject's actual body weight on the day of receiving the study drug (Day 1).
- ^h Height and weight will be measured at screening, and weight will be measured again before the single dose of study drug on Day 1.
- ⁱ Complete physical examination includes evaluations of 1) head, eyes, ears, nose, and throat; 2) cardiovascular; 3) dermatological; 4) musculoskeletal; 5) respiratory; 6) gastrointestinal; and 7) neurological systems. At subsequent visits (and as clinically indicated), limited, symptom-directed physical examinations will be performed.
- ^j At each timepoint, 3 consecutive 12-lead ECGs will be performed approximately 2 minutes apart to calculate heart rate and measure QT and QTcF intervals.
- ^k The cardiac telemetry will be performed from approximately 1 hour predose to 24 hours post dosing.

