- ^l After informed consent has been signed but prior to the administration of the study drug, only SAEs should be reported. After initiation of the study drug, all AEs and SAEs, regardless of relationship to study drug, will be reported until 30 days after the dose of study drug or EOS Visit, whichever is later. After the period, the investigator should report any SAEs that are considered to be related to the study drug.
- ^m Hematology, clinical chemistry and coagulation will be evaluated by a local laboratory. The list of hematology, clinical chemistry and coagulation parameters is provided in [Appendix 4](#).
- ⁿ Collect sample for urine analysis as well as urine microscopy. The urine microscopy will be performed if the urinalysis parameter, such as leukocyte esterase, is out of normal range.
- ^o During the screening, a urine sample will be collected for the screening of drugs; a breath test will be performed for the screening of alcohol.
- ^p Pregnancy test will be performed for female subjects of childbearing potential during the study. The serum pregnancy test will be performed at the Screening Visit, and the next serum pregnancy test will be conducted after the admission on Day -1 and before the dose of study drug on Day 1. Female subjects of childbearing potential with negative results will be eligible to receive the study drug. Afterwards, urine pregnancy test will be performed. A serum pregnancy test must be performed if the urine pregnancy test is positive or equivocal.

APPENDIX 2. SCHEDULE OF ASSESSMENTS FOR DAY 1

Study Day	Day 1				
	Predose	Dosing	1-hour postdose	6-hours postdose	12-hours postdose
BGB-DXP593 single dose administration		X			
Vital signs/ height and weight	X (- 15 min)		X (± 15 min)	X (± 15 min)	X (± 15 min)
Targeted physical examination	X (- 30 min)				
12-lead ECG	X (- 15 min)		X (± 15 min)	X (± 15 min)	X (± 15 min)
Cardiac telemetry	X				
Prior/Concomitant medications review	X				
Adverse event review	X				
Hematology	X (- 60 min)				
Clinical chemistry	X (- 60 min)				
Coagulation	X (- 60 min)				
Urinalysis	X (- 60 min)				

Abbreviations: ECG, electrocardiogram; min, minutes.

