6.2.2. Conventions

Unless otherwise specified, the following conventions will be applied to all analyses:

- 1 year = 365.25 days. Number of years is calculated as (days/365.25) rounded up to 1 significant digit.
- 1 month = 30.4375 days. Number of months is calculated as (days/30.4375) rounded up to 1 significant digit.
- Age will be calculated as the integer part of (date of informed consent date of birth + 1)/365.25.
- P-values will be rounded to 4 decimal places. P-values that round to 0.0000 will be presented as '< 0.0001' and p-values that round to 1.000 will be presented as '> 0.9999'.
- For laboratory results collected as ≥ x, the value of the laboratory results will be set as x. For laboratory results collected as < x, the value of the laboratory results will be set as x divided by 2.
- For by-visit observed data analyses, percentages will be calculated based on the number of subjects with non-missing data as the denominator, unless otherwise specified.
- Unscheduled measurements and retested measurements will not be included in byvisit table summaries and graphs but will contribute to the best/worst case value

where required (e.g., shift table). Listings will include scheduled, unscheduled and retest data.

- For continuous endpoints, summary statistics will include n, mean, standard deviation, median, Q1, Q3 and range (minimum and maximum).
- For discrete endpoints, summary statistics will include frequencies and percentages.

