6.2.3. Handling of Missing Data

Missing data will not be imputed unless otherwise specified elsewhere in this SAP. Missing dates or partially missing dates will be imputed conservatively for adverse events and prior/concomitant medications/procedures. Specific rules for the handling of missing or partially missing dates for adverse events and prior/concomitant medications/procedures are provided in Appendix A.

By-visit endpoints will be analyzed using observed data unless otherwise specified. For observed data analyses, missing data will not be imputed, and only the observed records will be included.

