6.5.5. Electrocardiograms (ECG)

Descriptive statistics for ECG parameters (heart rate and QTcF interval) and changes from baseline will be summarized by visit and dose level.

Subject data listings of each parameter will be provided. Abnormal values will be flagged and identified as those outside (above or below) the normal range. Reference (normal) ranges for ECG parameters are defined as following:

Heart rate: 60-100 bpmQTcF interval: ≤450 msec

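### Does the SAP's silence on averaging triplicate ECGs leave baseline QTcF and heart rate resting on a single tracing?

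*SAP*

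**What the plan says.** Protocol 8.2.4 requires that at each timepoint "3 consecutive 12-lead ECGs will be performed approximately 2 minutes apart to calculate heart rate and measure QT and QTcF intervals". Footnote j of Appendix 1 repeats this, and Appendix 2 places one of these timepoints within 15 minutes before the Day 1 dose. Exclusion criterion 12 (Protocol 4.2) applies to the average QTcF: "> 450 msec (based on triplicate ECGs").

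For the analysis, SAP 6.5.5 states: "Descriptive statistics for ECG parameters (heart rate and QTcF interval) and changes from baseline will be summarized by visit and dose level". The only baseline definition is the general one in SAP 6.2.1: "baseline is defined as the last non-missing value collected before the dose of study drug". Neither section mentions replicates, and neither does Protocol 10.3.5. The one SAP convention on repeated measurements (6.2.2) concerns a different kind: "Unscheduled measurements and retested measurements will not be included" in by-visit tables and graphs. SAP 6.2.3, on missing data, adds that for observed-data analyses "only the observed records will be included".

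**The concern.** Of the scheduled assessments, only the ECG is taken in replicate, so a baseline rule that works for laboratory values and vital signs is ambiguous here. If the database holds one record per tracing, the last value before dosing is the third predose tracing. Two of the three readings would then be discarded at the point where averaging helps most, because the same baseline is subtracted at every later timepoint.

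Change from baseline in ECG parameters is a named secondary endpoint, and each dose level has only 6 active subjects. One programmer might take the third tracing and another the mean, and both could claim to follow the SAP. A third might leave the replicates uncollapsed, giving 18 records for 6 subjects. The out-of-range flag for QTcF (normal at or below 450 ms) could likewise attach to a tracing or to a mean.

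**Working it through.** The plan states no figure on this point, so there is none to reproduce. The check has a textual part and a numerical part.

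**Which reading do the documents support?**

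- Protocol 8.2.4 gives the purpose of the three tracings as obtaining heart rate and QT/QTcF at the timepoint. That reads most naturally as one result from three tracings.
- Exclusion criterion 12 is the only place that says how triplicates are combined, and it averages them.
- Protocol 8.2.4 keeps the tracings in the site file. Neither document says whether the eCRF holds three readings or one averaged value. If it holds one, the SAP 6.2.1 rule already returns the average.
- The observed-records phrase in SAP 6.2.3 is a statement against imputation. It does not tell anyone to enter every replicate. SAP 6.2.2 counts subjects in the denominators of by-visit percentages. A table showing n = 3 × 6 = 18 in a group of 6 would be a visible programming error, not a fair reading of the plan.

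**How much would the literal reading cost?**

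Let s be the SD between readings within a triplicate and b the SD between timepoints within a subject. Both are assumptions. With independent errors of equal variance, and k readings averaged at each end:

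Var(change) = 2b² + s²/k_base + s²/k_post

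For s = b = 6 ms, with the SE of a 6-subject mean equal to SD/√6:

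| Value used | k_base | k_post | Variance | SD (ms) | SE, n = 6 (ms) |
|---|---|---|---|---|---|
| Mean at both ends | 3 | 3 | 72 + 12 + 12 = 96 | 9.80 | 4.00 |
| Third tracing at baseline, mean afterwards | 1 | 3 | 72 + 36 + 12 = 120 | 10.95 | 4.47 |
| Single tracing at both ends | 1 | 1 | 72 + 36 + 36 = 144 | 12.00 | 4.90 |

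The second row is a mixed case: someone who averages after dosing would most naturally average before it too. Its SD exceeds the first row's by 11.8% (√(120/96) = 1.118). The third row is the consistent literal reading, and the rise is 22.5% (√(144/96) = 1.225).

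Over s and b of 4 to 10 ms each, the extremes are:

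- s = 4, b = 10: variances 210.67, 221.33 and 232.00. The SD rises by 2.5% (mixed) or 4.9% (single throughout).
- s = 10, b = 4: variances 98.67, 165.33 and 232.00. The SD rises by 29.4% or 53.3%.

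**Would it bias the result?**

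The third reading minus the triplicate mean has expectation zero if readings do not drift across the three tracings. Its variance is s²(1 − 1/3), so its SD is s√(2/3). For the mean of 6 subjects this becomes s√(2/3)/√6 = s/3, which is 1.3 to 3.3 ms for s of 4 to 10 ms. This chance error recurs at all 16 scheduled post-dose timepoints (3 on Day 1 and 13 visits from Day 2 to Day 113) when the same 6 subjects contribute. It does not average out over visits, but it has no preferred direction.

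**What depends on the table?**

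- SAP sections 5 and 6.5 make the safety analysis descriptive, with no formal inference.
- The pausing criteria (Protocol 3.3) count related adverse events by grade and seriousness.
- The committee reviews 12-lead ECG data before escalation (Protocol 3.2.2.1), but no rule there uses a mean change from baseline.
- The investigator reviews every tracing (Protocol 8.2.4), and clinically significant ECG abnormalities are recorded as adverse events (Protocol 9.3.5), however the replicates are summarised.

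**The case for a change.** The best argument for a change is that the text is silent and one sentence would end the ambiguity at no cost in ECGs. The sponsor specified averaging for eligibility, so its absence from the analysis text is noticeable. A SAP that fixes decimal places for PK parameters could also define the ECG value. With 6 subjects, a baseline error repeated at 16 timepoints can look like a consistent shift. The flag can change too: invented predose readings of 440, 446 and 454 ms give a third tracing above 450 ms but a mean of 446.7 ms.

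The silence stands, and so does the possibility of the literal reading if tracings are stored one by one. The step from there to an unsound analysis does not stand. It needs tracing-level storage, which the documents do not show. It also needs an analyst who discards two of three planned replicates despite the eligibility precedent. The flag is a marker in a listing that a reader interprets next to the data, and the plan attaches no decision to it. If the database already carries one averaged value, the added sentence would only record existing practice.

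**Conclusion.** This is missing detail of a kind that analysts fill sensibly, and the plan does not need to change. The documents lean towards one averaged value per timepoint, and under that reading the SAP baseline rule gives the mean of the predose triplicate.

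If the literal reading were used, the cost would be precision in a descriptive table. In the s = b = 6 ms example, the SE of a 6-subject mean change goes from 4.00 ms to 4.47 ms with a single-tracing baseline, or to 4.90 ms with single tracings throughout. The loss is larger if readings vary much more within a triplicate than between timepoints. The absence of bias rests on there being no systematic drift across the three tracings. All SDs here are assumed, and the variance model takes replicate errors as independent and equal. No test, error rate, sample size or pausing decision would be altered.
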